2.2.1.2 Secondary efficacy variables

The secondary efficacy variables are as follows:

- Change from Baseline in Health Assessment Questionnaire - Disability Index (HAQ-DI) at Week 16
- Reduction of 90% from Baseline in Psoriasis Area and Severity index (PASI90 response) at Week 4 and Week 16 in the subgroup of subjects with PSO involving at least 3% of Body Surface Area (BSA) at Baseline
- Change from Baseline in the Short Form 36-item Health Survey (SF-36) Physical Component Summary (PCS) at Week 16
- Minimal Disease Activity (MDA) response at Week 16
- Change from Baseline in Van der Heijde modified Total Sharp Score (vdHmTSS) at Week 16 on subjects with elevated high sensitivity C-reactive protein (hs-CRP) and/or at least 1 bone erosion at Baseline
- Enthesitis-free state based on the Leeds Enthesitis Index (LEI) at Week 16 in the subgroup of subjects with enthesitis at Baseline in the pooled population of PA0010 and PA0011
- Dactylitis-free state based on the Leeds Dactylitis Index (LDI) at Week 16 in the subgroup of subjects with dactylitis at Baseline in the pooled population of PA0010 and PA0011
- Change from Baseline in vdHmTSS at Week 16
- ACR20 response at Week 16
- ACR70 response at Week 16
- Proportion of subjects with an Investigator Global Assessment (IGA) score of 0 (clear) or 1 (almost clear) and at least a 2-grade reduction from Baseline at Week 4 and Week 16 in the subset of subjects with psoriatic skin lesions at Baseline

- Change from Baseline in the Patient's Assessment of Arthritis Pain (PtAAP) at Week 16
- Enthesitis-free state based on the Spondyloarthritis Research Consortium of Canada (SPARCC) index at Week 16 in the subgroup of subjects with enthesitis at Baseline
- Change from Baseline in Psoriatic Arthritis Impact of Disease-12 (PsAID-12) total score at Week 16.

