4.2.2.1 Non-responder imputation

For binary endpoints, the non-responder imputation (NRI) analysis, also described above as the composite estimand, will consider the following subjects as “non-responders” for the timepoint of interest:

- Subjects with missing data at the time point of interest. In the case of ACR50, non-response is imputed if ACR50 cannot be derived (ie: derived as “missing”) based on available ACR components ([Section 8.1.1](#))
- Subjects who remained in the study at the timepoint of interest but discontinuing study treatment before the timepoint of interest (data after IE)
- Subjects with missing Baseline value (for composite or non-composite binary variables based on change(s) from Baseline of continuous endpoint(s)).

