- If a digit is recorded as affected and the circumference of the contralateral digit is missing, the normative value will be used for comparison with the affected digit.
- If a digit is selected but recorded as 'not affected' but has circumference and contralateral circumferences collected, a missing tenderness score will be considered as 1.
- If the investigator did not complete the LDI questionnaire at Baseline, it will be assumed that no digits were affected (ie, a LDI score of 0 will be assigned).

Dactylitis-free state is based on a Leeds Dactylitis Index (LDI) at Week 16 of 0, for subjects with dactylitis at Baseline ($LDI>0$).

Dactylitis-free state at Week 16 (pooled between PA0010 and PA0011) is the 8th endpoint in the sequential testing hierarchy (Table 4–5) and will be based on pooled data from PA0010 and PA0011 (for subjects in the BKZ160mg Q4W and the Placebo groups). The analysis will also be repeated using PA0010 data alone and the p-value will only be considered nominal.

A tender dactylitis count will be calculated as the sum of the tenderness scores for all digits and will be used for the PASDAS score calculation (Section 8.3.1.6).

8.2.1.8 Psoriasis Area Severity index 90 (PASI90) at Week 4 (in subjects with PSO involving at least 3% of BSA at Baseline)

This variable will be derived as described in Section 8.2.1.2.

8.2.1.9 ACR20 and ACR70 response at Week 16

The ACR20 and ACR70 responses are defined based on respectively 20% and 70% or greater improvement from Baseline in the same measures than the primary endpoint (Section 8.1.1).

8.2.1.10 Proportion of subjects with an Investigator Global Assessment (IGA) score of 0 (clear) or 1 (almost clear) AND at least a 2-grade reduction from Baseline at Week 4 and Week 16 in the subset of subjects with psoriatic skin lesions at Baseline

A static IGA for PSO will be used to assess disease severity in all subjects during the study. The Investigator will assess the overall severity of PSO using the following 5-point scale presented in [Table 8-4](#).

Table 8-4: Five-point IGA

Score	Short Descriptor	Detailed Descriptor
0	Clear	No signs of PSO; post-inflammatory hyperpigmentation may be present
1	Almost Clear	No thickening; normal to pink coloration; no to minimal focal scaling
2	Mild	Just detectable to mild thickening; pink to light red coloration; predominantly fine scaling
3	Moderate	Clearly distinguishable to moderate thickening; dull to bright red, moderate scaling

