4	Severe	Severe thickening with hard edges; bright to deep dark red coloration severe/coarse scaling covering almost all or all lesions

IGA=Investigator's Global Assessment; PSO=psoriasis

The IGA response is defined as clear [0] or almost clear [1] assessment with at least a 2-category improvement from Baseline, meaning that this parameter will be only evaluable for subjects with psoriatic skin lesions (IGA score ≥ 2) at Baseline.

Note that per protocol and device setting, only subjects with BSA $\geq 3\%$ at Baseline will have IGA assessed at post-Baseline visits.

For some subjects with BSA $\geq 3\%$ at Baseline, IGA data have not been captured at Week 4 and Week 16 visits when BSA $< 3\%$ at those visits. To address that, an additional supportive analysis will be performed in which these subjects will be considered as IGA responders at the respective visit.

8.2.1.11 Change from Baseline in the Patient's Assessment of Arthritis Pain (PtAAP) at Week 16

The change from Baseline at Week 16 in PtAAP will be analyzed as described in [Section 8.1.4.4](#).

8.2.1.12 Enthesitis-Free state based on Spondyloarthritis Research Consortium of Canada (SPARCC) index at Week 16

The SPARCC index measures the severity of enthesitis through the assessment of 16 sites, 8 for the right part and 8 for the left part of the body: the greater trochanter (right/left), quadriceps tendon insertion into the patella (right/left), patellar ligament insertion into the patella and tibial tuberosity (right/left), achilles tendon insertion (right/left), plantar fascia insertion (right/left), medial and lateral epicondyles (right/left), and the supraspinatus insertion (right/left). Tenderness on examination is recorded as either present (1) or absent (0) for each of the 16 sites, for an overall score range of 0 (no enthesitis) to 16 (severe enthesitis).

In case 9 or more are missing, the SPARCC index will be set to missing. If at least 8 items are available, the available items will be assessed and scored and then weighted by the number of the assessed items as shown in the formula below:

$$SPARCC\ index = n \times \frac{\sum_{i=1}^n score}{\sum_{i=1}^n AI}$$

where n refers to the number of total items and AI the number of assessed items.

The analysis of enthesitis-free state based on SPARCC index at Week 16 from Baseline will be restricted to the subset of subjects with enthesitis at Baseline (defined as SPARCC>0).

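### The IGA response subset has no BSA limit, yet IGA is followed only in subjects with Baseline BSA ≥3%, so NRI makes the remaining subjects non-responders by design

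*SAP*

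**What the plan says.** **Population.** Section 2.2.1.2 lists the secondary variable as IGA 0 or 1 with "at least a 2-grade reduction from Baseline at Week 4 and Week 16 in the subset of subjects with psoriatic skin lesions at Baseline". Section 8.2.1.10 makes this operational as Baseline IGA ≥2, "meaning that this parameter will be only evaluable for subjects with psoriatic skin lesions". Neither place sets a BSA threshold.

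**Collection.** Section 8.2.1.10 opens with "A static IGA for PSO will be used to assess disease severity in all subjects during the study". Later it reads "Note that per protocol and device setting, only subjects with BSA" of at least 3% "at Baseline will have IGA assessed at post-Baseline visits". It then reports that for some subjects who did have Baseline BSA ≥3%, "IGA data have not been captured at Week 4 and Week 16 visits when BSA" was below 3% at the visit.

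**Missing data.** Section 8.2.2 applies NRI to secondary binary endpoints. Section 4.2.2.1 lists, among those counted as non-responders, "Subjects with missing data at the time point of interest".

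**Other planned analyses.** For secondary binary endpoints outside the hierarchy, Table 4-2 also plans a modified composite analysis with MI and an observed-case analysis. Section 8.2.1 gives no method priority over another. Section 8.2.1.10 adds a supportive analysis that counts the skipped subjects with Baseline BSA ≥3% as responders. Section 8.3.1.10 repeats the definition and this supportive analysis for visits from Week 4 to Week 52.

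**The concern.** The denominator and the data collection do not match. A subject with Baseline IGA ≥2 and BSA <3% belongs to the subset but, by the collection rule, never has a post-Baseline IGA. NRI then fixes the outcome in advance. The reported rate is no longer the share of the stated population that reached clear or almost clear skin.

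The second problem is that improvement itself produces the missing value. In subjects with Baseline BSA ≥3%, IGA was in some cases not recorded because BSA had fallen below 3%, and NRI scores that visit as a failure.

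At stake are the reported IGA response rates and treatment contrasts at Weeks 4 and 16, and the by-visit rates in Section 8.3.1.10. Elsewhere the SAP deals with this kind of gap. PASI90 is limited to BSA ≥3% (Section 2.2.1.2), MDA has a rule for Baseline BSA <3 (Section 8.2.1.4), and a tender dactylitis count missing because Baseline LDI is 0 is set to 0 in PASDAS (Section 8.3.1.6). IGA has no rule for Baseline BSA <3%.

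**Working it through.** The SAP states no IGA rate or power, so there is no IGA figure to reproduce. Illustrative rates are borrowed from PASI90 in Section 2.4.2: 45% for bimekizumab and 10% for placebo. As a check on these inputs, the PASI90 power with 0.60 × 420 = 252 versus 0.60 × 280 = 168 subjects (two-sided 0.05, no continuity correction) exceeds 99.9%. This agrees with the stated figure of over 99%.

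**Symbols.**
- p: true response rate.
- f: share of the Baseline IGA ≥2 subset with Baseline BSA <3%. Not given; assumed over a range.
- s: share of true responders whose IGA was skipped at the visit. Not given; assumed, and taken as equal in both arms.
- u: share of true non-responders whose IGA was skipped. Not given; assumed.

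Subjects with BSA <3% are assumed to respond like the rest.

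**NRI rate** = p × (1 − f) × (1 − s). With f = 0 and s = 0 it returns 45% versus 10%: 35 points, OR (0.45/0.55)/(0.10/0.90) = 7.36.

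| f | s | Bimekizumab | Placebo | Difference | OR |
|---|---|---|---|---|---|
| 10% | 0 | 40.5% | 9.0% | 31.5 | 6.88 |
| 20% | 0 | 36.0% | 8.0% | 28.0 | 6.47 |
| 40% | 0 | 27.0% | 6.0% | 21.0 | 5.79 |
| 0 | 10% | 40.5% | 9.0% | 31.5 | 6.88 |
| 0 | 25% | 33.8% | 7.5% | 26.3 | 6.28 |
| 0 | 50% | 22.5% | 5.0% | 17.5 | 5.52 |
| 20% | 25% | 27.0% | 6.0% | 21.0 | 5.79 |

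**Where f might lie.** Section 2.4.2 assumes 60% of subjects have BSA ≥3%. Let g be the unknown share of the other 40% with IGA ≥2, and suppose every subject with BSA ≥3% has IGA ≥2. Then f = 0.40g/(0.60 + 0.40g). This gives 14.3% for g = 0.25, 25% for g = 0.50 and 33.3% for g = 0.75. The row f = 20% corresponds to g = 0.375.

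**What the other analyses do.**
- *All-responder supportive analysis.* Rate = (1 − f) × [p + (1 − p) × u]. It leaves the BSA <3% group as failures. With f = 20% and u = 0 it still shows 36% versus 8%. With f = 20% and u = 10% it shows 40.4% versus 15.2%: too low for bimekizumab and too high for placebo.
- *Observed cases.* Subjects with BSA <3% drop out, and so do the skipped improvers. If every skipped subject is a true responder, rate = p(1 − s)/(1 − ps). At s = 25% this is 38.0% versus 7.7%, a difference of 30.3 points.
- *MI.* The model in Section 4.2.2.2 contains region, bone erosion and the IGA values at Baseline and later visits. BSA, which decides whether IGA is recorded, is not in it. Read literally, subjects with BSA <3% would be imputed wholly from their Baseline IGA and strata, using the course of subjects with more extensive disease.

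**Bounds once f = 0.** With s = 25% and u = 10%, NRI gives 33.8% versus 7.5% and all-responder gives 50.5% versus 19.0%. Each arm's true rate (45%, 10%) lies between its two values. The true difference of 35 points does not lie between 26.3 and 31.5. The two analyses bound the rates but not the contrast.

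**The case against.** **The skipped visits are disclosed and bracketed.** This stands in part. The SAP names the problem, sets an all-responder analysis against NRI and adds a by-visit summary of BSA (Section 8.3.1.10). A reader might infer that the supportive analysis is the only remedy, or that skipped IGA values are never imputed. The SAP does not support that: Table 4-2 and Section 8.2.3 already plan MI and observed cases for this endpoint, with no method ranked above another. None of these corrects the NRI denominator, for the reasons shown in the working.

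**The sponsor may mean the subset to be BSA ≥3%.** The sentence on evaluability is soon followed by the collection note, so this may be the intention. If so, the structural part disappears. But the text gives IGA ≥2 as the only condition, and a programmer following it would include the BSA <3% subjects.

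**The size is assumed.** This stands. Neither f, s nor u is in the SAP, and the 60% is a PASI90 planning figure.

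**The consequence is limited.** This also stands. IGA is outside the hierarchy and its p-values are nominal (Section 8.2.2). The skin endpoint in the hierarchy, PASI90 at Week 16, is already limited to BSA ≥3%.

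**Conclusion.** The point holds. Followed as written, Sections 8.2.1.10, 8.2.2 and 4.2.2.1 give NRI rates in which every subject with Baseline IGA ≥2 and BSA <3% is a failure by design, and in which some improvers with Baseline BSA ≥3% are failures too. Both arms' rates fall and the difference shrinks: from 35 to 28 points in the illustration with 20% structural loss, and to 21 points if a quarter of true responders are also skipped. These figures rest on PASI90 rates standing in for IGA rates, on assumed f and s, on equal s in both arms, and on BSA <3% subjects responding like the rest.

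Two stronger readings are not supported. One is that a particular loss, or a greater proportional loss on bimekizumab, can be read from the SAP. It cannot, because the shares are not given. The other is that a trial conclusion is at risk or that the error favours bimekizumab. In the scenarios run, NRI works against bimekizumab, a large odds ratio remains, and no hypothesis in the hierarchy is touched.

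**What to change.** 1. In Sections 2.2.1.2, 8.2.1.10 and 8.3.1.10, define the IGA population as Baseline IGA ≥2 and Baseline BSA ≥3%, as is done for PASI90. List this in Section 3.10 if it departs from the protocol.
2. Reconcile the statement that IGA is assessed in all subjects with the statement that it is assessed after Baseline only where Baseline BSA was ≥3%.
3. For visits skipped because BSA was below 3%, present NRI and all-responder explicitly as lower and upper bounds on each arm's rate, and say that they do not bound the difference.
4. Add same-visit BSA to the planned IGA imputation model, and same-visit PASI only if it was collected when IGA was skipped. The SAP does not say that it was.

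The cost is SAP wording and a changed model for an MI run that is already planned. The analysed subset becomes smaller, and the result no longer describes subjects with skin lesions but BSA <3%, for whom no post-Baseline IGA exists under the stated collection rule.

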8.2.2 Primary analysis of secondary efficacy variables

The secondary efficacy variables will be analyzed for all subjects in the RS by treatment group (except for vdHmTSS for which the analysis will be performed on the RAS).

As indicated in [Table 4–5](#), there are 8 secondary endpoints included in the testing hierarchy that will be tested in a chronological order until one is failed to be statistically significant.

For the other secondary endpoints (secondary endpoints which are not part of the testing hierarchy), the p-values produced by the statistical models will be considered nominal since these endpoints are not controlled for multiplicity.

For the secondary composite and non-composite binary endpoints, the same estimand structure (composite estimand) as the one defined for the primary efficacy analysis of the primary efficacy endpoint ([Section 8.1.2](#)) will be used. The NRI approach for handling missing data and the same analysis model will be considered, and the analysis results will be presented similarly, with the exceptions that the analyses performed on pooled data from PA0010 and PA0011 subjects will consider the region and the study-id factor as possible covariates for the modelling.

The statistical hypothesis for the binary variables at Week 16 is that the conditional odds ratio in the BKZ group compared with placebo treatment group is equal to 1.

For the secondary continuous endpoints, the analysis will evaluate the hypothetical estimand as defined below:

- Population = Subjects enrolled according to the protocol-specified inclusion/exclusion criteria and randomized to IMP.
- Subject level outcome = variable as stated in [Section 2.2.1.2](#)
- IE handling = An IE is defined as discontinuation of study treatment prior to Week 16. A hypothetical strategy for addressing IE will be implemented. This estimand targets the treatment difference in a scenario where withdrawal from study treatment does not occur, such that outcomes for subjects without an IE are as observed, and outcomes for subjects with an IE are treated as though they had completed treatment through Week 16 but on Placebo. A MI strategy will be used to impute any missing data and observed data after IE which will be set to missing prior to running MI. Such data will be imputed using reference-based MI, in which the MI model is based on data from the Placebo group.
- Population-level summary measure = the difference in the adjusted means between BKZ 160mg Q4W and placebo.

The same analysis model and imputation strategy for handling missing data as in [Section 8.1.4.4](#) will also be considered. The analysis results will be presented similarly as for this analysis on the individual ACR components.

For vdHmTSS, a similar estimand structure as the one defined above for continuous endpoints will be used with the following exception for population:

- When analyzing change at Week 16 from Baseline in vdHmTSS for subjects with elevated hs-CRP or with at least one bone erosion at Baseline: Population=Subjects enrolled according to the protocol-specified inclusion/exclusion criteria, randomized to IMP, who have a valid radiographic image of the hands and feet at Baseline in the subgroup of patients with elevated CRP and with at least one bone erosion at Baseline.

- When analyzing change at Week 16 from Baseline in vdHmTSS for all subjects:
Population=Subjects enrolled according to the protocol-specified inclusion/exclusion criteria, randomized to IMP, who have a valid radiographic image of the hands and feet at Baseline.

In the case of MDA as the response is based on 7 different component scores, it is necessary to consider various data scenarios that could impact the calculation of response. The rules described here are applicable in the context of the calculation of MDA response and may differ from the rules applied for calculating and summarizing the components individually (some values may need to be imputed for component analysis but are not required here to evaluate MDA response).

The following rules will be applied to complete the derivation of MDA response based on the composite estimand definition:

- If a given visit has been preceded by an IE (treatment discontinuation):
 - The endpoint at all subsequent visits (whether the data were observed or not) will be set to “non-response” as the subject has not met the criteria for response.
- If a given visit has not been preceded by an IE:
 - If a subject is satisfying at least 5 of the 7 MDA criteria, the subject will be considered as MDA responder
 - If a subject is not satisfying at least 3 MDA criteria, the subject will be considered as MDA non-responder
 - In all other cases, the NRI approach will be applied.

An overview table will combine the results of the primary analysis for the primary and secondary efficacy endpoints included in the testing hierarchy.

For the country specific analyses performed on subjects randomized in Japan, the region factor will not be considered as a covariate for the modelling.

Considering that the number of subjects randomized in Japan is low (less of 10% of the Randomized Set), statistical models might not converge. If a model (Logistic Model or Mixed model) is not converging, all related adjusted statistics and p-value will not be presented, “NE” for “Not Evaluable” will be displayed instead.

